14. INTERIM ANALYSIS

There is no interim analysis in this study.

15. DATA MONITORING/REVIEW COMMITTEE

There is no data monitoring committee for this study.

16. COMPUTER METHODS

Statistical analyses will be performed using Version 9.2 (or higher) of SAS® on a suitably qualified environment.

17. CHANGES TO ANALYSES SPECIFIED IN PROTOCOL

Since a decision has been made to early terminate the trial, an abbreviated Clinical Study Report (CSR) will be generated, which will contain a full report of information related to safety and abbreviated summary of efficacy evaluation. The majority of the efficacy analyses outlined in section 9.8, efficacy analysis section of the protocol will not be conducted. No hypothesis testing will be performed on any of the efficacy endpoint. Only descriptive statistics will be generated for clinical resolution status and adenoviral eradication status as outlined in section 10.2 of this SAP.

18. DATA HANDLING CONVENTIONS

18.1 General Data Reporting Conventions

Continuous variables will be summarized using the following descriptive statistics: number of subjects (n), mean, median, SD, minimum, maximum unless otherwise specified. Categorical and count variables will be summarized by the number of subjects (n), frequency and the percent of subjects in each category unless otherwise specified. Percentages will be presented with one decimal point.

See TFLs4Shire for rules on the number of decimal places to present data and p-values.

18.2 Study Visits and Windows

CRF visits will be used in all summary tables and listings.

Study day will be calculated as follows:

- If the assessment date is on or after the date of first instillation:

Study day = assessment date – first dosing date + 1

- If the assessment date is before the date of first instillation:

Study day = assessment date – first dosing date

18.3 Derived Efficacy Endpoints

Clinical resolution is defined as absence of bulbar conjunctival injection and watery conjunctival discharge. Bulbar Conjunctival Injection will be assessed based on a 0-4 scale which uses pictures from the Validated Bulbar Redness (VBR) Scale. Watery Conjunctival Discharge will be assessed based on a 0-3 scale. For both bulbar conjunctival injection and watery conjunctival discharge, 0 score indicates normal or none and a higher score indicates a higher severity of the clinical sign. A 0 sum of bulbar conjunctival injection score and watery conjunctival discharge score represents reaching clinical resolution. Any non 0 sum means not reaching clinical resolution. If either individual score is missing, clinical resolution status will be set to missing.

Adenoviral eradication is defined as negative CC-IFA (indeterminate CC-IFA result is considered negative CC-IFA). Positive CC-IFA is considered not reaching adenoviral eradication. If an eye has missing CC-IFA result at baseline, the eye will be assumed to be CC-IFA negative at baseline for determination of the study eye.

Global clinical score is defined as the sum of bulbar conjunctival injection score and watery conjunctival discharge score. If either individual score is missing, global clinical score will be set to missing.

Modified clinical resolution is defined as a global clinical score of 0 or 1. All other scores are considered not reaching modified clinical resolution. If either individual score is missing, modified clinical resolution status will be set to missing.

Expanded clinical resolution is defined as a global clinical score of 0, 1, or 2 with neither bulbar conjunctival injection score nor watery conjunctival discharge score having a score of 2. Otherwise, the subject is considered not reaching expanded clinical resolution. If either individual score is missing, expanded clinical resolution status will be set to missing.

Time to clinical resolution will be derived based upon assessments at Visits 2 (Day 3), 3 (Day 6), 4 (Day 8), and 5 (Day 12) in the study eye. Time to clinical resolution will equal to the study day corresponding to the visit when the subject first reaches clinical resolution in the study eye.

Cross over infection status will be assessed by CC-IFA results as follows:

Scenario		Cross-over Infection Status at Post Baseline Visit
Both eyes CC-IFA positive at baseline		Not applicable
Only one eye CC-IFA positive at baseline	The other eye CC-IFA positive at post baseline visit	Yes
	The other eye CC-IFA negative at post baseline visit	No
Both eyes CC-IFA negative at baseline		Not applicable

Ocular discomfort total score (in the version for adult and older children) is defined as the sum of eye pain score, the feeling that something was in your eye score and itching score. If any individual score is missing, then ocular discomfort total score will be set to missing.

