#### **7.2.2.2 Adenoviral Eradication**

Adenoviral eradication for an eye is defined as negative CC-IFA in that eye. CC-IFA for each eye will be conducted using conjunctival swab samples collected at each visit. See the Laboratory Manual for further details.

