#### **7.2.3.6 Microbiology Laboratory Evaluations**

All laboratory assays will be performed according to the laboratory’s normal procedures.

All bioanalytical assays for the study will be validated following FDA/ICH guidelines, based on the method’s intended use. The lab will only receive sample ID numbers and collection dates, the lab results will then be transferred to the central lab for data analysis. The lab will not receive any information on subject treatment assignment.

The following laboratory assessments will be performed:

- Cell Culture Assay (CC-IFA): This test will be performed on samples collected at all visits to determine the presence of adenovirus.
- quantitative Polymerase Chain Reaction (qPCR): This test will be performed on all CC-IFA positive samples at all visits to determine viral count.
- Adenoviral serotyping: This test will be done at baseline only to determine what serotypes of adenovirus are present.
- qPCR: This test will be performed on samples for qualitative detection of HSV at baseline (Visit 1).

One swab sample from each eye will be taken from inferior conjunctival cul-de-sac at all study visits for adenoviral testing. For neonates and infants <2 months of age, PCR testing for qualitative detection of chlamydia and gonorrhea at baseline will also be conducted using the baseline visit sample. Qualitative PCR: This test will be performed on samples from baseline visit (Visit 1) for HSV testing.

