4.4 Modified Intent to Treat (mITT) population

The mITT Population consists of a subset of the ITT population who receive at least one dose of investigational product and have a positive CC-IFA adenovirus test at baseline in the study eye.

Analyses conducted using the ITT and mITT populations will be based upon the treatment assigned while analyses conducted using the Safety Analysis Set will be based upon the treatment received.

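### An indeterminate CC-IFA result after baseline is scored as adenoviral eradication, and no listed table title shows how many such results there are

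*SAP*

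**What the plan says.** SAP 18.3 (Derived Efficacy Endpoints) places the rule inside the endpoint definition: "Adenoviral eradication is defined as negative CC-IFA (indeterminate CC-IFA result is considered negative CC-IFA". The next sentence gives the only failing result: "Positive CC-IFA is considered not reaching adenoviral eradication". The rule for a missing result in the same paragraph is restricted in time and purpose: "the eye will be assumed to be CC-IFA negative at baseline for determination of the study eye". The indeterminate rule has no such restriction.

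Under SAP 4.4, mITT subjects must "have a positive CC-IFA adenovirus test at baseline in the study eye". SAP 10.2 summarises eradication status by treatment group at each visit in the mITT, with exact binomial 95% confidence intervals. The output is Table 14.2.1.2. SAP 2.6, 10.2 and 17 rule out any efficacy hypothesis test because the study stopped early.

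Protocol 7.2.2.2 (Amendment 4) says: "Adenoviral eradication for an eye is defined as negative CC-IFA in that eye". It does not mention indeterminate results and leaves assay details elsewhere: "See the Laboratory Manual for further details". The SAP follows Amendment 5, which was not available. On the evidence here the SAP fills a gap in the protocol and does not contradict it.

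**The concern.** A baseline-positive eye with an indeterminate result later has not been shown to be free of virus, yet it is scored as a success. Compared with scoring it as not eradicated or as missing, this rule can only raise the reported proportion.

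The plan has no second viral measure on the same swab to settle the matter. Protocol 7.2.3.6 says of quantitative PCR for adenovirus: "This test will be performed on all CC-IFA positive samples at all visits to determine viral count". An indeterminate sample therefore gets none. CC-IFA itself is repeated ("This test will be performed on samples collected at all visits to determine the presence of adenovirus"), so later swabs give indirect evidence for Days 3, 6 and 8. Day 12 is the last visit and has no later swab.

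With testing dropped, the proportions and their intervals are the efficacy result, and Table 14.2.1.2 is one of three efficacy tables in SAP 21. No listed table title mentions indeterminate results, so a reader of the table may not be able to tell how many eyes counted as eradicated had no clear negative.

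**Working it through.** **Does the rule apply after baseline?** Three parts of the SAP settle this.

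- The rule is part of the definition of an endpoint assessed only after baseline (Days 3, 6, 8 and 12, SAP 10.2).
- The neighbouring missing-result rule is limited to baseline and the indeterminate rule is not.
- Only a positive result counts as not eradicated. An indeterminate result in an mITT study eye at any later visit is therefore scored as eradicated.

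No other section gives a different rule or a sensitivity analysis for indeterminate results.

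**Where the denominator comes from.** Protocol 9.6 and SAP 2.5 plan 92 mITT subjects per arm for 90% power (31% vs 11% clinical resolution, two-sided Fisher's exact test at 5%). Exact enumeration gives 90.1%, so the planned figure reproduces. It serves here only as an illustrative n, because the study stopped early.

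**Effect per result.** Let x be the clear negatives, k the indeterminate results and n the eyes in the arm.

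- SAP rule: (x + k)/n
- Counted as not eradicated: x/n
- Set to missing: x/(n − k)

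The SAP rule exceeds the not-eradicated rule by k/n. Per result this is 1/92 = 1.1 points, 1/60 = 1.7 points (assumed n) or 1/30 = 3.3 points (assumed n).

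**Illustration.** The documents give no eradication rate and no indeterminate rate, so x = 28 and every k are assumptions, with n = 92. Intervals are Clopper-Pearson 95%.

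| k | SAP rule | Not eradicated | Missing |
|---|---|---|---|
| 1 | 29/92 = 31.5% (22.2–42.0) | 28/92 = 30.4% (21.3–40.9) | 28/91 = 30.8% (21.5–41.3) |
| 3 | 31/92 = 33.7% (24.2–44.3) | 30.4% (21.3–40.9) | 28/89 = 31.5% (22.0–42.2) |
| 5 | 33/92 = 35.9% (26.1–46.5) | 30.4% (21.3–40.9) | 28/87 = 32.2% (22.6–43.1) |
| 10 | 38/92 = 41.3% (31.1–52.1) | 30.4% (21.3–40.9) | 28/82 = 34.1% (24.0–45.4) |

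The gap between the first two rules does not depend on x. With an assumed x = 46 and k = 5, the SAP rule gives 51/92 = 55.4% (44.7–65.8) against 46/92 = 50.0% (39.4–60.6), again 5/92 = 5.4 points.

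**Which rule is nearest the truth?** Assume true eradication e = 30%, a share u = 5% of eyes indeterminate, and clear calls correct.

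- All indeterminate eyes still infected: SAP rule e + u = 35.0%; missing e/(1 − u) = 31.6%; not eradicated e = 30.0%.
- All indeterminate eyes clear: SAP rule e = 30.0%; missing (e − u)/(1 − u) = 26.3%; not eradicated e − u = 25.0%.

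No rule is right in both cases. If t of the k indeterminate eyes are truly clear, the true proportion in the sample is (x + t)/n with 0 ≤ t ≤ k. It always lies between the not-eradicated figure and the SAP figure. The missing figure gives no such bound: in the second case it falls below the truth, and in the first above it.

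**The case against.** The strongest reply is that this is an openly stated rule and not an error. Indeterminate may be the laboratory's term for a culture in which adenovirus was not confirmed. The rule would then be accurate and the added row would understate eradication. The rule is also consistent over time: only a confirmed positive counts as infected, for mITT entry and afterwards. The added row would treat the same result as not infected at baseline and as not eradicated later. The rule applies equally to both arms, the laboratory has no treatment information, and nothing is tested. Nothing shows that there is even one indeterminate result. At n = 92 the interval is about 20 points wide, far more than one to three results can move the estimate. Table and listing specifications are in a separate document (SAP 1), so a footnote or Listing 16.2.6.3 may already show the raw results.

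Most of this is correct, and it limits the point to a minor one. It rules out any claim about bias between arms and any demand that the main rule change. What remains is that uncertain results are resolved in the favourable direction with no stated reason and no alternative classification in either document. A subject listing, even if it shows raw results, gives no proportions or intervals. The inconsistency between baseline and follow-up is a reason to show both rows and not to replace one with the other. The cross-over derivation uses the same positive/negative split, but SAP 10.2 does not summarise that endpoint by treatment group.

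**Conclusion.** The concern holds, as a minor one. As written, every post-baseline indeterminate CC-IFA result in an mITT study eye is reported as eradication in Table 14.2.1.2, including the key secondary endpoint at Day 6. Compared with counting such results as not eradicated, the reported proportion rises by k/n, which is 1.1 points per result at the planned 92 per arm and more in a smaller arm. Only descriptive proportions and their exact intervals are affected.

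The total effect and any direction between arms cannot be determined, because the frequency and meaning of indeterminate are not given. That the two rows bracket the truth rests on clear positive and negative calls being correct. Confidence is medium: Amendment 5, the Laboratory Manual and the table specifications were not available.

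**What to change.** Before unmasking, add two things to Table 14.2.1.2:

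1. The number of indeterminate CC-IFA results by arm and visit.
2. Beside the current rule, a row with exact 95% confidence interval in which post-baseline indeterminate results count as not eradicated.

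A third row with these results set to missing is optional. It would need a stated denominator, because SAP 18.3 has no rule for a missing CC-IFA after baseline. The sponsor should choose the main row and justify it from the laboratory's definition of indeterminate. The baseline use of the rule, for study-eye selection and mITT entry, can stay as written.

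The cost is one SAP sentence and a few table rows from the exact-binomial code already in SAP 20.1. The added row may show a less favourable figure, and it understates eradication if the indeterminate eyes are in fact clear. If there are no indeterminate results, the rows coincide and a footnote is enough.

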18.4 Repeated or Unscheduled Assessments of Safety Parameters

Assessments obtained on the scheduled CRF visits will be included in summary tables. Additional repeated or unscheduled assessments will not be included in the by visit summary tables, but will be included in subject listings.

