#### 7.2.3.2 Slit Lamp Biomicroscopy

Slit lamp biomicroscopy (or hand held slit lamp) will be performed during the study as outlined in [Table 1](#). Magnification of the slit lamp will be consistent with standard clinical practice. The subject will be seated.

Observations will be graded as Normal or Abnormal. Abnormal findings will be described, and clinically significant abnormalities should be recorded in the source and on the electronic CRF (eCRF) (in Medical History at Screening; any changes from the screening visit may be recorded as adverse events by the investigator). Please note the investigator may use his/her discretion to determine whether Not Clinically Significant (NCS) and disease progression should be considered AEs). The following will be examined at each visit:

- Lids
- Conjunctiva
- Cornea
- Anterior Chamber
- Iris

- Lens

For infants and young children, if the above exams cannot be performed with a slit lamp or a hand held slit lamp, an external examination is to be conducted in accordance with American Academy of Pediatrics (AAP) Policy Statement for Visual System Assessment in Infants, Children, and Young Adults by Pediatricians ([Donahue and Baker, 2016](#); [American Academy of Pediatrics, 2016](#); located in the Study Operations Manual). The examination of lens in these subjects should be conducted at Visit 1 and Visit 5 (or ET visit) and graded based on the external examination and red reflex exam (Section [7.2.3.4](#)). All other structures listed above will be examined and graded at all visits based on the external examination. Observations will be graded as Normal or Abnormal. Abnormal findings will be described.

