11.1 Adverse Events

AEs will be coded using MedDRA version 19.1. Any AE that occurs after the first dose of investigational product instillation will be considered a treatment- emergent adverse event (TEAE).

An overall summary of the number of subjects with TEAEs will be presented, including the number and percentage of subjects with any TEAEs, ocular TEAEs, non-ocular TEAEs, TEAEs leading to death, serious TEAEs, TEAEs related to investigational product and TEAEs leading to discontinuation of investigational product as well as the total number of events in each category.

The number and percentage of subjects reporting TEAEs in each treatment group and across all subjects will be tabulated by System Organ Class (SOC) and Preferred Term (PT) as well as by SOC, PT, and maximum severity. TEAEs considered related to investigational product will also be summarized by SOC and PT. If more than 1 AE occurs with the same SOC/PT for the same subject, then the subject will be counted only once for that SOC/PT using the most severe and most related occurrence for the summarization by severity and by relationship to investigational product, respectively. The incidence of common TEAEs ($\geq 5\%$ of subjects in any treatment group) will also be summarized by SOC and PT. Serious TEAEs, TEAEs leading to discontinuation of investigational product and TEAEs leading to death, will be summarized by SOC, PT and treatment group and across all subjects. The number and percentage of subjects reporting local tolerability TEAEs (overall, related to IP and not related to IP) in each treatment group and across all subjects will also be tabulated by SOC and PT. PTs that are considered to be local tolerability AEs will be provided by global drug safety (GDS) before database lock. Separate tables will be generated for ocular TEAEs and non-ocular TEAEs. For all above tables, ocular TEAEs will be summarized at subject level and also by study eye, fellow eye and both eyes.

Listings of all TEAEs will be provided by subject.

Pre-treatment events (captured on the AE form that occurred prior to the first dose of investigational product) will be listed by subject but not tabulated.

Imputed dates, severity and relationship (see Section 18.7, 18.8 and 18.9 respectively for imputation rules) to investigational product will be marked in the listings.

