11.2 Other Safety Variables

The following safety measures will be descriptively summarized by study eye and fellow eye and by treatment group and across all subjects at each visit:

- Best corrected visual acuity (BCVA, logMAR scoring) and change from baseline BCVA
- Slit lamp biomicroscopy (normal, abnormal – not clinically significant, abnormal – clinically significant) for 6 anatomic anterior segment regions: lids, conjunctiva, cornea, iris, anterior chamber and lens
- Intraocular Pressure (raw score and change from baseline score)
- Non-dilated/ Dilated Fundus examination (normal, abnormal – not clinically significant, abnormal – clinically significant) for 3 anatomic posterior segment regions: vitreous, optic nerve and macula
- Red reflex examination (normal, abnormal– not clinically significant, abnormal – clinically significant) for infants and small children in whom a fundus examination cannot be done

Continuous endpoints will be summarized by number of subjects (n), mean, median, SD, SE, minimum and maximum. Binary endpoints will be summarized by number of subjects (n), frequency and percentage.

BCVA/change from baseline BCVA and slit lamp biomicroscopy at each visit as well as non-dilated/ dilated fundus examination (or red reflex exam for infants and small children in whom a fundus examination cannot be done), intraocular pressure and pregnancy test results at visits 1 and 5/early termination will be provided by subject in Safety Population in data listings. A by subject listing will also be generated for chlamydia and gonorrhea results at Visit 1 in Safety Population in subjects less than 2 month of age and for Herpes Simplex Virus (HSV) at Visit 1 in Safety Population.

**12. CLINICAL PHARMACOKINETIC AND
PHARMACODYNAMIC ANALYSES**

N/A.

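### The by-visit slit-lamp and acuity tables leave out unscheduled examinations and no worst-post-baseline summary is planned, so a finding seen only there reaches a by-arm table only as an AE

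*SAP*

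**What the plan says.** SAP 18.4 sets the rule for the examination tables: "Assessments obtained on the scheduled CRF visits will be included in summary tables". It then adds: "Additional repeated or unscheduled assessments will not be included in the by visit summary tables, but will be included in subject listings".

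SAP 11.2 says that acuity, slit lamp, intraocular pressure, fundus and red reflex will be "descriptively summarized by study eye and fellow eye and by treatment group and across all subjects at each visit". The table list in SAP 21 matches: Tables 14.3.6.1 to 14.3.6.5 are all by visit, and none reports a worst or any-time value.

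Adverse events are handled separately, in tables that are not by visit. SAP 11.1 counts any AE after the first dose as treatment-emergent and states: "Serious TEAEs, TEAEs leading to discontinuation of investigational product and TEAEs leading to death, will be summarized by SOC, PT and treatment group".

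The protocol links examinations to AEs in two different ways. Section 7.2.3.1 says that clinically significant acuity changes should be entered as AEs. Section 7.2.3.2, on the slit lamp, says "any changes from the screening visit may be recorded as adverse events by the investigator", and adds a note giving the investigator discretion over findings that are not clinically significant and over disease progression.

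SAP 17 cuts efficacy back after early termination but promises an abbreviated report "which will contain a full report of information related to safety".

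**The concern.** Unscheduled examinations are usually made because something has changed in the eye, so they are likely to hold some of the more informative safety readings. Under SAP 18.4 they appear only in subject listings. If the eye has recovered by the next scheduled visit, Tables 14.3.6.1 and 14.3.6.2 show the recovered eye, and no other planned examination table holds the abnormal one.

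The AE tables are then the only by-arm route. For slit-lamp changes that route depends on each investigator's decision. At stake is whether a short-lived corneal or conjunctival change can be compared between arms, in a report where safety is the part still to be given in full.

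**Working it through.** The plan gives no figure on this point, so there is none to reproduce, and the sample-size calculation is not an input. The check traces where a finding would appear and then asks how short-lived it must be to escape the by-visit tables.

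**Step 1. Where a post-dose slit-lamp or acuity finding appears** (SAP 11.1, 11.2, 18.2, 18.4 and 21):

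| How the finding is captured | By-visit Tables 14.3.6.1 and 14.3.6.2 | AE tables by arm | Listings |
|---|---|---|---|
| At a scheduled visit | Yes | If recorded as an AE | Yes |
| At an examination entered as Visit 5 or early termination | Yes | If recorded as an AE | Yes |
| Only at an unscheduled examination, recorded as an AE | No | Yes | Yes |
| Only at an unscheduled examination, not recorded as an AE | No | No | Yes |

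Only the last row has no by-arm summary. In the third row the event is counted by preferred term and severity, but the slit-lamp grade or logMAR change is not summarised.

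**Step 2. Can the last row occur?**

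- Slit lamp: yes. Protocol 7.2.3.2 permits AE recording of changes rather than requiring it. Protocol 8.1.4 keeps expected disease progression out of AEs. Protocol 4.4 allows withdrawal for lack of improvement or for worsening, and 4.4.1 lists lack of efficacy and physician decision as reasons separate from adverse event. A stop under one of those reasons, with no AE recorded, would show by arm in disposition, but the examination grade would be only in Listing 16.2.8.2.
- Acuity: less readily. Protocol 7.2.3.1 directs that clinically significant changes become AEs, so the last row should be confined to changes not judged clinically significant.

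**Step 3. How long could a finding last and still be missed?** Both examinations are scheduled at all five visits. The windows in Table 1 are: Visit 2, Day 3 to 4; Visit 3, Day 6; Visit 4, Day 8 to 9; Visit 5, Day 12 to 14. Longest gap = latest day of the next visit minus earliest day of the current one, taking baseline as Day 1.

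- Visit 1 to 2: 4 − 1 = 3 days
- Visit 2 to 3: 6 − 3 = 3 days
- Visit 3 to 4: 9 − 6 = 3 days
- Visit 4 to 5: 14 − 8 = 6 days

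A subject on schedule is missed during the dosing week only if the finding appears and clears within about 3 days. A subject who stops product goes to Visit 5 whenever possible (Table 1, note b). The documents fix no interval for that visit, so these gaps do not bound the discontinued subject.

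**Step 4. How many findings?** This cannot be computed. The documents give no rate of unscheduled examinations and no rate of findings confined to them. The planned 142 per arm need not be the number analysed, because the trial stopped early.

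**The case against.** A reader might infer that SAP 18.4 removes unscheduled findings from the safety tables altogether, so that the reading that made a subject stop product goes uncounted once the eye recovers. The documents do not support that.

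- The rule covers by-visit tables only. It does not govern the AE tables.
- An AE that leads to stopping is counted by arm in Table 14.3.2.3.1 or 14.3.2.3.2 and listed in 16.2.7.6. Later recovery does not remove it.
- Ocular AEs are also summarised by study eye, fellow eye and both eyes.
- If the stopping examination is entered as Visit 5 or early termination, it is in the by-visit table, because SAP 18.2 tabulates by CRF visit.
- The acuity route to an AE is firm. For slit lamp, the explicit discretion note concerns non-significant findings and disease progression, while protocol 8.1 defines an AE broadly and 8.1.4 asks for significant worsening of symptoms to be recorded. Many clinically significant corneal findings should therefore become AEs.

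A reader might also infer a bias in favour of one arm. That would need more unscheduled-only findings in that arm, and the documents give no data on this.

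Two further objections have force. Limiting by-visit rows to scheduled visits is sound practice, since it keeps the number of readings comparable between arms. And SAP 17's promise of full safety reporting does not commit the sponsor to worst-value tables; listings can form part of it.

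What survives is narrow: for a slit-lamp change not recorded as an AE, no planned table gives a by-arm count, and even for one recorded as an AE, no table gives the worst grade.

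**Conclusion.** The point holds in a limited form. Unscheduled readings are absent from Tables 14.3.6.1 and 14.3.6.2, no worst-post-baseline summary replaces them, and their only by-arm route is AE reporting, which is discretionary for slit-lamp changes. The gap is more material for slit lamp than for acuity. Its size is unknown, and the short intervals between scheduled visits suggest that it may be small for subjects who keep to the schedule. This is a cheap improvement, not a flaw that undermines the safety report.

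The conclusion assumes that early-termination examinations are entered under Visit 5, as SAP 11.2 implies by pairing the two. It also assumes that protocol 7.2.3.1 and 7.2.3.2 read the same in Amendment 5, which the SAP cites; the protocol reviewed here is Amendment 4.

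**What to change.** Leave SAP 18.4 and the by-visit rows as they are. Add to SAP 11.2 a worst-post-baseline summary by study eye, fellow eye and treatment group that uses every post-dose examination, including unscheduled and early-termination ones:

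- Table 14.3.6.2: for each of the six structures, the worst category reached (normal; abnormal, not clinically significant; abnormal, clinically significant).
- Table 14.3.6.1: the worst logMAR change from baseline.

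State whether examinations made after study exit to follow an unresolved AE (SAP Table 1, note k) are included. Add a footnote that subjects with more examinations have more chances of an abnormal reading, so the row should be read beside the by-visit rows.

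The cost is a few sentences in the SAP and one derived summary in each of two tables, from data already collected and listed. The only drawback is the unequal number of examinations, which the footnote discloses.
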